4.1. Sample Size

The sample size is based on clinical considerations to inform dose regimen decisions for continued clinical development.

Approximately 180 participants will be enrolled in this Phase 1 study, 5 dose-level cohorts (Cohorts 1 to 5) each comprising 2 age groups. Cohorts 6 and 7 will comprise 1 age group (younger adults). With 30 participants in each cohort, there is a 78.5% probability to observe at least 1 AE if the incidence rate is 5% and a 95.8% probability to observe at least 1 AE if the incidence rate is 10%. With 30 participants in each cohort, a 10% unevaluable rate for immunogenicity results, and a standard deviation of 0.45 for log10-transformed increase from day 1, the ratio of the upper limit of a 2-sided 95% CI and the point estimate of geometric mean increase (GMI) is 1.5. The sample size in Cohorts 6 and 7 is based on clinical feasibility rather than on statistical rationale. With 15 participants in each cohort, there is a 79.4% probability to observe at least one AE if the true incidence rate is 10%.

4.2. Randomization, Stratification, and Blinding

Participants in Part A will be assigned sequentially to a dose-level cohort by age group. Participants in Part B will be randomly assigned on day 1 to receive study vaccine by dose-level cohort.

The study will be open label.

4.3. Analysis Set

The following analysis sets have been defined: Enrolled Set, Per protocol Immunogenicity Set, and Safety Set.

4.3.1. Enrolled Set

The Enrolled Set will include all eligible participants who gave informed consent, regardless of the participants' treatment status in the study.

4.3.2. Per protocol Immunogenicity (PPI) Set

The PPI Set includes all eligible participants who received a dose of study IP per protocol and who have values for predose and Day 15 neutralizing Ab titers against pseudovirus bearing S protein from the Omicron BA1 variant of SARS-CoV-2. Results from a blood sample deviating from the dosing or blood sampling schedule and results from a blood sample after intercurrent conditions that may interfere with immunogenicity (e.g., laboratory-confirmed SARS-CoV-2 infections or immunosuppressive or immunodeficient conditions) or after a prohibited concomitant medication/vaccination (COVID-19 vaccination) will be excluded from the PPI Set. The data will be analyzed according to the dose that participants received at Visit 1.

The PPI Set will be used for the immunogenicity analyses.

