### 7.3 Analysis Sets

The following analysis sets will be used in the statistical analyses:

- Enrolled Set: All eligible participants who gave informed consent, regardless of the participants' treatment status in the study.
- Safety Set: All participants who receive 1 dose of IP. The Safety Set will be used for all analyses of safety. Data are analyzed according to treatment received. The Safety Set will be used for safety analyses.

- Per Protocol Immunogenicity Set: The PPI Set includes all eligible participants who received a dose of study IP per protocol and who have values for predose and Day 15 neutralizing Ab titers against pseudovirus bearing S protein from the Omicron variant of SARS-CoV-2. Results from a blood sample deviating from the dosing or blood sampling schedule ([Table 13-1](#)) and results from a blood sample after intercurrent conditions that may interfere with immunogenicity (eg, laboratory-confirmed SARS-CoV-2 infections or immunosuppressive or immunodeficient conditions) or after a prohibited concomitant medication/vaccination (COVID-19 vaccination) will be excluded from the PPI Set. The analysis will be done according to the dose that participants received at Visit 1. The PPI Set will be used for the immunogenicity analyses.

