5.2. Protocol Deviations

Major protocol deviations are a subset of protocol deviations that may significantly impact the completeness, accuracy, or reliability of the study data or that may significantly affect a participant's rights, safety, or well-being. Major protocol deviations rules will be developed and finalized before database lock.

Major protocol deviations include, but are not limited to, the following:

- Study vaccine not administered at all
- Invalid/missing informed consent
- Fraudulent data
- Administration of concomitant vaccine(s) forbidden in the protocol
- Participants got vaccinated but not as per protocol

- Vaccine storage temperature deviation which is not accepted by quality
- Expired vaccine administered
- Ineligible participant
- Administration of any medication forbidden by the protocol
- Participants did not comply with blood sample schedule
- Serological results not available pre and post-vaccination (day 15 and day 29) for neutralizing Abs against pseudovirus bearing S protein from Omicron BA.1 SARS-CoV-2
- Serological results available but results unreliable (e.g. wrong blood sample management)
- Intercurrent condition impacting immunogenicity

The number of participants with major protocol deviations will be summarized by dose group. Major protocol deviations will be listed with date of occurrence, deviation description, and analysis set from which participant is excluded. Major protocol deviation summary will be based on the Enrolled Set.

The major protocol deviations will be listed by age group, dose group, participant number and reported in the CSR.

6. Demographics and Baseline Characteristics

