The GMT at each postvaccination time point, the GMI from baseline, and the 95% CIs in all cohorts will be analyzed using an ANCOVA model on log10 transformed titers with dose group and age group as fixed in the model and prior Covid-19 infection and prevaccination baseline value as covariates.

[figure not shown]
8.2.2. Seroresponse rate 28 days after the booster dose (day 29), based on neutralizing Ab titers against pseudoviruses bearing S protein from SARS-CoV-2 WT, Omicron BA.1, BA.2 and BA.5 variants at each collection timepoint, with seroresponse defined as postboost titers $\geq 4 \times$ preboost titers.

Proportion of participants with neutralizing seroresponse of serum SARS-CoV-2 WT, Omicron BA.1, BA.2 and BA.5 variants specific Ab from baseline at day 29 by dose group and prior Covid-19 infection will be tabulated with 2-sided 95% Clopper Pearson CIs. The same summaries will be generated for seroresponse rate 14 days after booster dose (Day 15) as supportive analyses.

[figure not shown]
CCI

CCI

CCI

Approved

CCI

9 Safety Analysis

Safety, tolerability, and reactogenicity will be assessed by clinical review of all relevant parameters including solicited and unsolicited AEs, SAEs, AESIs, MAAEs, AEs leading to withdrawal from study participation, safety laboratory test results, vital signs, and physical examination findings.

All safety analyses will be based on Safety Set. All safety analyses will be provided by dose group and age group unless otherwise specified.

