9.5 Electrocardiogram

At screening and at the Day 8 visit, all participants will be assessed by 12-lead ECG for evidence of asymptomatic myocarditis or pericarditis. The results of the electrocardiogram findings will be listed by participants and dose group, and sorted by age group, dose group and participant number.

10 Pharmacokinetics

Not applicable.

11 Pharmacodynamics

Not applicable.

12 Interim Analysis

There are 2 planned interim analyses of safety and immunogenicity data for at least neutralizing Ab titers against SARS-CoV-2 WT, Omicron BA.1 or BA.5 variant pseudoviruses. A first interim analysis of safety and immunogenicity data covering at least neutralizing Ab titers against pseudovirus bearing S protein from WT, Omicron BA.1 or BA.5 SARS-CoV-2 up to 14 days after study vaccine administration in participants enrolled in Cohorts 1, 2, and 3 will be performed including at least day 1 and day 15 data. A second interim analysis of safety and immunogenicity data covering at least neutralizing Ab titers against pseudovirus bearing S protein from WT, Omicron BA.1, or BA.5 SARS-CoV-2 will be performed 14 days after participants in Cohorts 4 and 5 have received study vaccine including at least day 1 and day 15 data in Cohorts 4 and 5 and day 29 data in addition in Cohorts 1,2 and 3.

Further to the above the first interim will be based on the PNA data. Available binding IgG data at the time of the first interim will be included, but it is not requested to have 100% of these data at the time of the first interim analysis. For PNA, BA.1, BA.5 and Wuhan (ancestral strain, comparator with CV2CoV) will be prioritized (priority #1). BA.2 can be done as priority #2. Regarding cohort 6 and 7 (lowest doses), it is unsure at this stage whether these cohorts will be enrolled as it will depend on the data generated at 12 mcg.

The safety set will be used for the interim immunogenicity analyses.

13 Changes in the Planned Analysis

Because the assays are not fully validated values below LLOQ or above ULOQ they will be used as released. Results released as below a value will be assigned 0.5*the value. Results released as above a value will be assigned the value.

14 References

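### In the final per-protocol immunogenicity analyses, a missing Day 15 Omicron BA.1 titre removes a participant's valid Day 29, 91 and 181 results for every strain, including the Day 29 seroresponse endpoint

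*SAP*

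**What the plan says.** Protocol 7.3 admits to the PPI Set eligible participants dosed per protocol "who have values for predose and Day 15 neutralizing Ab titers against pseudovirus bearing S protein from the Omicron variant of SARS-CoV-2". SAP 4.3.2 repeats the condition and names BA.1 as the strain, admitting those "who have values for predose and Day 15 neutralizing Ab titers against pseudovirus bearing S protein from the Omicron BA1 variant of SARS-CoV-2". It then states: "The PPI Set will be used for the immunogenicity analyses". Neither document defines a visit-specific or strain-specific version of the set.

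The endpoints cover more than Day 15 and BA.1. SAP 8.2.1 analyses GMTs and GMIs at Days 15, 29, 91 and 181 for WT, BA.1, BA.2 and BA.5. SAP 8.2.2 sets the seroresponse analysis as "Proportion of participants with neutralizing seroresponse of serum SARS-CoV-2 WT, Omicron BA.1, BA.2 and BA.5 variants specific Ab from baseline at day 29" and treats Day 15 seroresponse as supportive only.

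Three other provisions matter:

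- SAP section 12 says of the interims: "The safety set will be used for the interim immunogenicity analyses". The second interim takes in "day 29 data in addition in Cohorts 1,2 and 3".
- SAP 8.2.1 bases the supporting listings on the Enrolled Set.
- SAP 5.2 lists among the major deviations: "Serological results not available pre and post-vaccination (day 15 and day 29) for neutralizing Abs against pseudovirus" (for BA.1).

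**The concern.** The condition for entering the set is tied to one visit and one strain, but the set is used for four post-booster visits and four strains. If a Day 15 sample is missed or fails in the laboratory, the participant's Day 29 titre is no less valid. Under the rule as written, that titre still leaves the Day 29 seroresponse and GMI analyses, and so do the participant's WT, BA.2 and BA.5 results.

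The rule also sits oddly in its own paragraph. The other PPI exclusions in SAP 4.3.2 (off-schedule samples, samples after infection or after a prohibited vaccination) are written for individual sample results. The Day 15 condition is the only visit-based one that acts on the whole participant.

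Two practical consequences follow:

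- **Interim versus final.** A Day 29 result from Cohorts 1-3 shown at the second interim, which uses the Safety Set, could be absent from the final Day 29 summary.
- **Out-of-window Day 15 samples.** The schedule allows ±3 days. A sample drawn on Day 19 is off schedule, so its result is excluded. The SAP does not say whether that participant still counts as having a Day 15 value. If not, one late draw removes all later visits.

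What is at stake is some precision in small groups, and some selection if participants without a Day 15 value respond differently.

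**Working it through.** **Inputs from the documents** (SAP 4.1; Protocol 7.2): 30 participants per Part A cohort, 15 per Part B cohort, 10% unevaluable for immunogenicity, and SD 0.45 for the log10 increase from Day 1. The stated ratio of the upper 95% limit to the GMI is 1.5.

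**Reproducing the plan's figure.** Ratio = 10^(t(0.975, n−1) × 0.45/√n). With n = 30 × 0.9 = 27, the ratio is 1.507 (1.478 with a normal quantile). Both round to the stated 1.5.

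**Assumptions.** The documents give no Day 15-specific missingness, so I take 5%, 10% and 20%, independent of Day 29 missingness. The plan's 10% is applied at Day 29.

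**Day 29, cohort of 30.** A visit-specific set keeps 27. With the Day 15 condition, n = 27 × (1 − Day 15 missingness):

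| Day 15 missing | Evaluable n at Day 29 | Valid Day 29 results left out | Ratio (n rounded) |
|---|---|---|---|
| 0% | 27 | 0 | 1.507 (27) |
| 5% | 27 × 0.95 = 25.65 | 1.35 | 1.520 (26) |
| 10% | 27 × 0.90 = 24.3 | 2.7 | 1.549 (24) |
| 20% | 27 × 0.80 = 21.6 | 5.4 | 1.583 (22) |

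If the same people miss both visits, the loss is 0 whatever the rate.

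**Part B cohort of 15, 10% Day 15 missing.** 15 × 0.9 = 13.5 falls to 13.5 × 0.9 = 12.15. The ratio moves from 1.819 (n = 14) to 1.932 (n = 12).

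**Seroresponse interval (95% Clopper-Pearson, rate assumed near 60%).** At 16/27 the interval is 38.8-77.6%. At 14/24 (10% missing) it is 36.6-77.9%.

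**Selection.** The shift in the estimated seroresponse rate is (share of Day 29-evaluable participants left out) × (difference in rate between those kept and those left out). With 10% left out and an assumed difference of 10 to 30 points, the shift is 0.10 × 10 = 1 point to 0.10 × 30 = 3 points.

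**The case against.** The best defence has four parts.

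- **A common set is a legitimate choice.** Tying eligibility to the vaccine-strain response at Day 15, the interim time point, gives one eligibility rule at every visit. That is true. It does not explain why the Day 29 endpoint should depend on a visit whose own seroresponse is only supportive.
- **Independence is unfavourable to the plan.** Withdrawal before Day 15 also means no Day 29 sample. Infection or a prohibited vaccination before Day 15 excludes the later samples too. A missing predose titre excludes the participant under any sensible rule. This stands: the extra loss comes mainly from isolated missed, failed or possibly off-schedule Day 15 samples.
- **The effect is small.** At 10% the ratio moves from 1.507 to 1.549. Neither document plans a hypothesis test, so no power or error rate changes. This stands as well.
- **The data are not lost.** Results remain in the Enrolled Set listings, and participants left out of a set are listed with the reason.

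A reader might infer more than the documents support:

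- **That every immunogenicity analysis is affected.** The interims use the Safety Set. SAP 8.3 and 8.4 are largely redacted, so nothing specific to them can be checked.
- **That SAP 5.2 sets a second, stricter PPI rule requiring both Day 15 and Day 29.** It is a list of deviations. The bullet names no analysis set, its wording can also mean that both visits are missing, and the detailed deviation rules are still to be finalised before database lock. It needs clarifying, but a second rule is not shown, and neither is any further loss at Day 91 or 181 computed from one.
- **That the 10% unevaluable allowance is used up twice.** SAP 4.1 gives a single rate, not a rate per visit. The planned 27 may already be net of PPI exclusions.

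**Conclusion.** The point holds for the final PPI analyses. As written, a participant with valid predose and later titres is left out at Days 29, 91 and 181, for every strain, when only the Day 15 BA.1 titre is missing. Participants who have the required values are unaffected.

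The size is modest and cannot be forecast from the documents. With 5-20% independent Day 15 missingness, about 1.4 to 5.4 valid Day 29 results are left out per cohort of 30, and the GMI ratio is 1.52-1.58 instead of 1.51. With fully overlapping missingness there is no loss. The seroresponse interval barely changes at 10%, and a 1-3 point shift requires the assumed difference in response. The case for change rests less on these figures than on the mismatch between a Day 15, single-strain condition and later, multi-strain endpoints, which rewording can remove.

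**What to change.** 1. In SAP 4.3.2, define PPI eligibility per visit and per strain: an eligible participant dosed per protocol contributes at a visit when the predose titre and that visit's titre for the strain analysed are valid and no sample-level exclusion applies. This extends the logic already used for the other exclusions in that section. It also settles how an out-of-window Day 15 sample counts: it affects Day 15 only.
2. In SAP 5.2, reword the bullet on missing Day 15 and Day 29 serology to match, and say which visit's analysis it affects.
3. Protocol 7.3 carries the same Day 15 condition, so record the departure in SAP section 13. Changing SAP 4.3.2 alone would leave the two documents in conflict.

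The cost is wording, with no new data or procedures. The downside is that n differs by visit and strain, so each table should show its own n.

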4.3.3. Safety Set

All participants who receive 1 dose of IP. The Safety Set will be used for all analyses of safety. Data are analyzed according to treatment received.

5. Participant Disposition

5.1. Disposition

Participant disposition will be summarized by dose group for all participants. The number and percentage of participants for the following categories will be presented: participants who were enrolled, vaccinated, participants who discontinued from the study (i.e. did not complete the day 181 visit), participants in the Enrolled Set, PPI Set and Safety Set.

A participant may withdraw or be withdrawn from the study for any of the following reasons:

- Participant request.
- Investigator request.
- The participant is noncompliant with the protocol.
- The participant has a serious or intolerable AE(s) that, in the investigator's opinion, requires withdrawal from the study.
- The participant is lost to follow-up.

- Death.
- The sponsor terminates the study.
- The participant has safety laboratory results that reveal clinically significant hematological or biochemical changes from the baseline values, per investigator judgment
- The participant has symptoms or an intercurrent illness not consistent with the protocol requirements or that justify withdrawal
- Other reasons (e.g., pregnancy, development of contraindications of use of the IP)
- The participant withdraws consent, or the investigator or sponsor decides to discontinue their participation in the study withdrawal of consent by participant or the investigator or sponsor decides to discontinue their participation in the study

Participant status summary will also be provided which include participants who completed each visit, participants vaccinated with study vaccine, participants who had immunogenicity results at applicable visit, and participants who completed the study. Participant status summary will be also presented by dose and age group.

Participant disposition and discontinuation data will be presented in a listing sorted by age, dose group and participant number.

The number of participants included in each analysis set will be summarized. A listing of participants in each analysis set will also be provided by age, dose group and participant number. Participants excluded from the analysis sets will be listed with reason for exclusion(s) and sorted by age, dose group and participant number.

The primary reason for study discontinuation includes: Withdrawal due to AE, Lost To Follow-up, Physician Decision, Pregnancy, Site Terminated by Sponsor, Study Terminated by Sponsor, Withdrawal of Consent by Participant, Protocol Deviation, Vaccine Not Administered, Death, Other.

5.2. Protocol Deviations

Major protocol deviations are a subset of protocol deviations that may significantly impact the completeness, accuracy, or reliability of the study data or that may significantly affect a participant's rights, safety, or well-being. Major protocol deviations rules will be developed and finalized before database lock.

Major protocol deviations include, but are not limited to, the following:

- Study vaccine not administered at all
- Invalid/missing informed consent
- Fraudulent data
- Administration of concomitant vaccine(s) forbidden in the protocol
- Participants got vaccinated but not as per protocol

- Vaccine storage temperature deviation which is not accepted by quality
- Expired vaccine administered
- Ineligible participant
- Administration of any medication forbidden by the protocol
- Participants did not comply with blood sample schedule
- Serological results not available pre and post-vaccination (day 15 and day 29) for neutralizing Abs against pseudovirus bearing S protein from Omicron BA.1 SARS-CoV-2
- Serological results available but results unreliable (e.g. wrong blood sample management)
- Intercurrent condition impacting immunogenicity

The number of participants with major protocol deviations will be summarized by dose group. Major protocol deviations will be listed with date of occurrence, deviation description, and analysis set from which participant is excluded. Major protocol deviation summary will be based on the Enrolled Set.

The major protocol deviations will be listed by age group, dose group, participant number and reported in the CSR.

6. Demographics and Baseline Characteristics

6.1. Demographics

A summary of demographics and baseline information will be presented by dose group in each age group. The demographic characteristics consist of age (years), gender at birth, ethnicity, and race. The baseline characteristics consist of height (cm), weight (kg), BMI (kg/m^2), N protein, and prior Covid-19 infection, defined as either self reported Covid-19 infection or a positive N protein result from the last result/test prior to vaccination.

Descriptive statistics (mean, standard deviation, median, minimum and maximum) for age, height, weight, and BMI will be provided by study vaccine in each age group and overall.

The number and percentage of participants will be provided for gender at birth, ethnicity, race, prior Covid-19 infection and baseline N protein status by dose group in each age group and overall.

Percentages will be based on the total number of participants in the analysis set defined in the output.

Participant demographic and baseline characteristics will be sorted by age group, dose group and participant number, including child-bearing potential (applicable only for women).

6.2. Baseline Disease Characteristics

Not applicable

6.3. Medical History

6.3.1. General Medical History

Medical history will be coded using the latest version of Medical Dictionary for Regulatory Activities (MedDRA). The number and percentage of participants with any medical history, medical history that ended before Visit 1, and medical history that is still ongoing at Visit 1 (at the time of first vaccination) will be summarized overall and for each system organ class (SOC) and preferred term (PT) by dose group. Percentages will be calculated based on safety set.

Participant medical history data including specific details will be presented in a listing sorted by age group, dose group and participant number.

6.4. Inclusion and Exclusion Criteria

Enrolled participants who failed any inclusion/met any exclusion criteria will be classed as major protocol deviations.

7. Treatments and Medications

7.1. Prior and Concomitant Medications

All medications/vaccination will be coded according to the World Health Organization (WHO) drug dictionary (WHODrug), which will be updated whenever available throughout the study.

